## **RESEARCH DESIGN AND METHODS**

This study will have **two phases**, each with different study designs:

**Phase 1** will cover the period while individuals are waiting for care. The design of this phase is a randomized clinical trial, wherein participants are randomly assigned to one of three study conditions that vary by the type of Mobile Health (mHealth) intervention they can receive.

**Phase 2** begins when a participant has a first appointment for outpatient mental health care, and uses a cohort study design for measuring outcomes associated with clinic-based treatments.

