### Surveys

Participants will be asked to complete four surveys, including a baseline survey at the time of enrollment and three follow-up surveys, which will be designed to complement in-clinic assessments completed as a part of standard outpatient mental health care. To the extent possible, redundancy with in-clinic assessments (i.e., due to the Measurement-Based Care program) will be avoided. The first follow-up survey will occur at the end of 6 weeks post-enrollment, the second at the end of 18 weeks post-enrollment and the third at the end of 12 months post-enrollment.

Depending on waitlist length for outpatient mental health services, there may be variation in whether participants have engaged with clinical care by the time they complete their follow-up survey(s). Surveys will be administered by the predetermined schedule regardless of whether participants have engaged with care. The rationale for this decision, rather than scheduling follow-up surveys to coincide with the initiation of outpatient care:

1. There is a possibility that participants may never engage with outpatient care, and these non-engagers would never receive follow-up surveys
2. Waitlist time often varies between recruitment sites (i.e., UHS tends to have a shorter waitlist for care), which would create measurement biases (e.g., UHS patients may consistently engage in care with less time to engage with the app-based intervention)
3. Participants may be receiving other mental health care (e.g., via primary care), making it less important to time follow-up surveys with the initiation of outpatient mental health services
4. The existing timeline ensures all participants randomized to the groups receiving app-based interventions have received a reasonable 'dose' of the intervention prior to assessment
5. The existing timeline ensures that measurement will take place at generally the same time frame for all participants

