## **Screening and Recruitment**

Participant screening and recruitment will be managed by study staff. All study team members are required to complete team/study training and all appropriate regulatory training and disclosures.

The study will recruit 4,500 participants via patients at Michigan Medicine and student patients at University Health Service (UHS). Potential study participants will include adult patients (age 18+) that are scheduled for an intake mental health appointment, pre-screening mental health appointment, on the waitlist/referral list, or identified as a potential patient seeking mental health at either Michigan Medicine or UHS. These appointments are generally scheduled with a 3-10 week waiting period. Patients will be invited to participate in the study as soon as possible after scheduling their appointment in order to best maximize participation during their full waiting period.

A waiver of HIPAA authorization is requested in order for study staff to:

- 1) Receive daily lists of patients for whom a mental health intake appointment has been scheduled at each recruitment site
- 2) Access the Michigan Medicine and UHS electronic health records to confirm eligibility of listed patients and obtain contact information

Study staff will employ the following **recruitment strategies** to contact, screen, and enroll potential participants:

1. At the time of scheduling their intake mental health appointment, patients may be informed by call center staff that they may be contacted about a new study.

2. Daily lists of newly scheduled appointments and individuals on the waitlist/referral list will be generated by the Michigan Medicine Department of Psychiatry call center, UHS scheduling, or from the Research Data Warehouse (RDW) and provided to study staff.
3. Using existing Research Data Warehouse information, a patient is prospectively identified as someone who meets the study criteria during the screening process. Potentially eligible patients may be contacted by email/text message/phone call to introduce the study, with an invitation to contact the study team by phone or email if interested in participating.
4. Prior to contacting patients by phone/text message/phone call, study staff will complete preliminary screenings via listed patients' electronic health records to determine whether basic, objective inclusion criteria are met (e.g., scheduled outpatient mental health appointment, age 18+).

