### ***Self-Report Surveys***

Participants will complete four surveys, including a baseline survey and three follow-up surveys. All surveys will be self-administered via the MyDataHelps study app. In the case of technological difficulties, the study team does have paper copies of the baseline and follow-up surveys available, and the surveys may be administered in person or by phone. The baseline survey will take about 25 minutes. Survey questions include demographics, overall physical and mental health symptoms and diagnoses, substance use, environment, use of mobile technology and health apps, and social network and support. For each of the three follow-up assessments, participants will complete an approximate 20-minute survey with similar content as the baseline survey. If necessary, the survey can be administered by study staff via phone who will read survey questions to the participant and record their responses. When participants are due for their surveys, they will receive an email or app notification that their survey is available via the MyDataHelps app. If participants do not respond to the questionnaires, and have not indicated that they do not wish to participate in the study, a reminder will be sent by email, phone, mail, or text message.

The first follow-up survey will occur at the end of 6 weeks post-enrollment, the second at the end of 18 weeks post-enrollment, and the third at the end of 12 months post-enrollment. Each of these time-points may occur near the time of an in-person outpatient mental health clinic appointment, at which participants may be asked to answer some of the same questions that are contained in the study surveys. To reduce participant burden, study staff will monitor upcoming appointments and participants will receive a version of the survey without redundant items if they have an appointment within 1 week of their follow-up survey due date. They will still complete the remainder of the follow-up survey and be paid the same amount for their time. Additionally, participants who do not show for clinic appointments will still be able to complete the follow-up assessments via standard study procedure.

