### *App-Based Interventions*

Participants randomized to the groups receiving the apps will be asked to install an mHealth app onto their smartphone. The two apps that will be used are Headspace, an app designed to train the user in mindfulness practices, and Silvercloud, an app designed to deliver cognitive behavioral therapy. These apps were selected because of evidence of efficacy and applicability across a wide range of mental health symptoms. Participants receiving apps will be computer-assigned to receive one of the two options. Participants who were recruited with <2 weeks prior to their scheduled appointment (and thus not included in the initial randomization) will receive access to one of the two apps at the time of their intake appointment, also based on computer random assignment.

App notifications will encourage participants to use the apps regularly. If user data indicates that a participant is not using the apps, study staff will contact the participant via app notification, phone call, email, letter, or text message. SilverCloud allows for integration of a health coach as a supportive role for increasing engagement, largely through asynchronous messaging. Study staff will be trained in the role of the health coach and will engage with participants through the app to promote app use, personalization, and overall engagement. For both apps, study staff will provide ongoing technical assistance and address any participant barriers to app use.

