### **ANALYSIS PLAN**

A primary goal is to obtain information about the feasibility and acceptability of the use of app-based interventions and enhanced feedback in response to mobile health device use, as well as to estimate the distribution and variability of potential primary and secondary outcomes of interest. Data will be examined using standard univariate summary measures, bivariate statistical tests of association, and graphical displays. We will assess subjective and objective data in areas including mental health and physical health measures, substance use, and app use. This will assess responsiveness to the interventions as well as how best to provide clinicians with useful patient data that may help inform treatment decisions. This is a primary outcome for future work. Additional outcomes to be assessed are listed in Table 1.

We will calculate means and standard deviations for participant characteristics and outcomes measures at each assessment and also for change scores. With outcomes that are categorical, we will use the Chi square test, and with outcomes that are continuous, we will use t-tests to make comparisons.

We will also conduct baseline and ongoing analyses of the presence of genotype x stress interaction among this sample. For example, as a baseline analysis, we will investigate association between each variant/haplotype and PHQ (baseline) scores using linear regression. To explore gene x environment interactions, we will assess for association between each variant/haplotype and PHQ (change) scores.

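### The arm comparisons default to participants with an observed score, and neither baseline nor other collected data are given a role in handling missing ones

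*Combined protocol and SAP*

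**What the plan says.** Everything on analysis is in the ANALYSIS PLAN section of the combined protocol and SAP. It promises means and standard deviations for "outcomes measures at each assessment and also for change scores", and then: "With outcomes that are categorical, we will use the Chi square test, and with outcomes that are continuous, we will use t-tests". It names no analysis population, covariates, missing-data method, sensitivity analysis or comparison of responders with non-responders.

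Non-reply is dealt with operationally. In Self-Report Surveys, the passage that begins "If participants do not respond to the questionnaires" leads to a reminder. The same section allows staff to read the survey over the phone, and paper or in-person completion when technology fails. No expected response rate is given, overall or by arm.

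Some items are missing by design. The Surveys section says that, as far as possible, "redundancy with in-clinic assessments (i.e., due to the Measurement-Based Care program) will be avoided". Self-Report Surveys puts this into practice: a participant with an appointment within 1 week of the due date receives a survey without the overlapping items. No rule says how the clinic scores are brought into the outcome.

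The arms differ in features that could affect response. Under App-Based Interventions, "If user data indicates that a participant is not using the apps, study staff will contact the participant", and SilverCloud users may also have a staff health coach. Enhanced feedback is delivered inside MyDataHelps, the app that also delivers the surveys.

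Other data are collected on separate schedules: daily mood (Measures), wearable, phone and app-use data (Data Collected from Phones and Sensors) and health records (Electronic Health Record Data). No section links them to missing survey scores.

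**The concern.** Aim 1 asks about the independent and combined effectiveness of the interventions, in a trial where "participants are randomly assigned to one of three study conditions". A t-test or chi-square test at 6 weeks, 18 weeks or 12 months compares those who have a score, not those who were randomised. If people without a score differ in outcome from those with one, and either the response rate or the size of that difference varies by arm, two equally effective interventions will appear to differ.

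The target is large ("The study will recruit 4,500 participants via patients at Michigan Medicine"), so standard errors are small and a bias of a few tenths of a point can matter. Completing the baseline survey is a condition of enrolment, so baseline PHQ-9 and GAD-7 should be available for nearly everyone enrolled. The planned tests use baseline only through the change scores of those who respond later. For participants caught by the 1-week rule, the overlapping score can be absent even though the survey was returned.

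**Working it through.** The plan gives no power calculation, SD, response rate or allocation ratio, so there is no stated figure to reproduce. What follows is an illustration.

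**Inputs.** From the documents: 4,500 participants and three arms. Assumed: 1:1:1 allocation, so 4,500 / 3 = 1,500 per arm; PHQ-9 SD 6; two-sided alpha 0.05; true difference zero.

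**Formulas.** Let m be the proportion without a score and g the amount by which non-responders are worse than responders.
- An arm's available-case mean differs from its full mean by m × g. With g equal in both arms, bias b = g × (m1 − m2).
- SE = 6 × √(1/n1 + 1/n2), where n is the number observed.
- Type I error = Φ(−1.96 + b/SE) + Φ(−1.96 − b/SE).

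**Base case: 30% v 20% missing, g = 2.**
- b = 2 × 0.10 = 0.20 points, or 0.20 / 6 = 0.033 SD.
- Observed n = 1,050 and 1,200, so SE = 6 × √(1/1050 + 1/1200) = 0.254.
- b/SE = 0.79, so type I error = Φ(−1.17) + Φ(−2.75) = 0.121 + 0.003 = 12.4%.

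**Range.**

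| Missing | g | Bias | SE | Type I error |
|---|---|---|---|---|
| any gap | 0 | 0 | – | 5% |
| 30% v 25% | 2 | 0.10 | 0.257 | 6.7% |
| 30% v 20% | 1 | 0.10 | 0.254 | 6.8% |
| 30% v 20% | 2 | 0.20 | 0.254 | 12.4% |
| 40% v 25% | 3 | 0.45 | 0.268 | 38.9% |

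**Equal response does not guarantee safety.** With 30% missing in both arms but g = 0 in one and g = 2 in the other, b = 0.30 × 2 − 0.30 × 0 = 0.60, SE = 6 × √(2/1050) = 0.262, and the type I error is 63%.

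**How far auxiliary data could help.** A large simulated sample used response of 80% v 60%, with non-response driven by daily mood and a mood–PHQ-9 correlation of 0.4 to 0.6.
- Responder-only bias was about 0.26 to 0.41 points.
- Imputing from mood cut it to 0.01–0.02 when mood was known for every non-responder, and to 0.11–0.20 when it was known for half.
- When non-response also depended directly on the score, responder-only bias was about 0.57 to 0.68, and 0.24–0.30 remained even with mood known for everyone.

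Imputation therefore helps in proportion to how much auxiliary data exist, and it does not remove the need for a sensitivity analysis.

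**The case against.** Several stronger readings are tempting, and the documents do not support them.

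- **That the plan excludes non-responders by rule.** It does not. Available-case analysis is what the named tests do when nothing else is said. For people with a nearby clinic visit, the design implies that clinic scores stand in.
- **That mood, sensor and clinic data exist for many non-responders.** No section says so. Daily mood is entered in the same app as the surveys, so a person who stops opening it may lose both. Voluntary withdrawal ends data collection (WITHDRAWING). The Surveys section accepts that some participants may never engage with outpatient care.
- **That staff contact exists only in the app arms, so response will favour them.** Configuration outreach (Required Device Configuration), survey reminders and phone completion (Self-Report Surveys) and technical help (STUDY SUPPORT) cover all arms. Only non-use outreach and the coach are specific to the app arms, and both app arms receive them. Enhanced feedback sits in the survey app and could push response the other way. The direction is unclear.
- **That bias is certain.** It needs non-response to be related to outcome. Without that, the error rate stays at 5%.
- **That imputation would also bring a large gain in precision.** The proportionate saving in the variance of an arm mean is the fraction missing times R². That gives 12% to 24% for R² of 0.3 to 0.6, but only with 40% missing and auxiliary data on everyone.

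The plan also describes a primary goal as feasibility and says it will "estimate the distribution and variability of potential primary and secondary outcomes of interest", so it is not written wholly as a confirmatory trial. That softens the consequence, but Aim 1 is still comparative.

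What stands on this side is that the size of the problem is unknown and may be small. It does not supply a missing-data method or a rule for merging clinic scores.

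**Conclusion.** The concern holds in a limited form. As written, the Aim 1 comparisons default to available cases. No source of information already collected is given a role in handling missing scores, and the 1-week rule adds missing items without a merging rule. Response could differ by arm, in an unclear direction.

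If non-response is related to outcome, the base illustration gives a bias of 0.20 PHQ-9 points and a type I error of about 12%. Error rates run from 5% (no relation to outcome) to 39% (40% v 25% missing, 3 points) with a common gap in both arms, and are higher if the gap differs by arm. For scale, 1,500 per arm detects about 0.10 SD, or 0.6 points, with 80% power, so the base-case bias is about a third of the smallest detectable difference. The SD, allocation, response rates and gaps are all assumptions. The change is worth making because it is cheap, not because bias has been shown.

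**What to change.** In ANALYSIS PLAN, for the Aim 1 comparisons of PHQ-9 and GAD-7:

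1. Replace the available-case tests with an analysis of all randomised participants, using multiple imputation done separately by arm. Include baseline and earlier survey scores and, where available, summaries of mood, sensor and app-use data before the due date. Imputing by arm allows mood ratings to relate differently to PHQ-9 under enhanced feedback.
2. Use the clinic score for any item omitted under the 1-week rule, and treat the item as missing if no clinic score was recorded.
3. Add a delta-adjusted sensitivity analysis in which non-responders are worse by, for example, 0 to 3 PHQ-9 points, varied separately by arm, because imputation removes only the bias that observed data explain.
4. Report response by arm at each survey.

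State who counts as randomised first. Phase 1 says that recruits with under 2 weeks' wait are still randomised to the three groups, whereas App-Based Interventions says they are outside the initial randomisation.

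The cost is SAP wording and programming, with no new data collection. The downside is more analysis work, and a smaller gain if the auxiliary data are also missing for non-responders. Other valid missing-data methods exist; what matters is that one is specified in advance.

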### OBJECTIVES

As part of the Precision Health initiative at the University of Michigan, this project is focused on the effects of wearable and mobile technology to both reduce mental health symptoms and predict response to clinic-based treatments.

The overall goal of this project is to reduce the burden of mental health conditions by two means:

- 1) Increasing capacity in the mental health care system through expanding use of mobile technology-delivered interventions.
- 2) Accelerating recovery by matching patients to the pharmacological, psychological, and mobile-based treatments from which they will likely derive the greatest benefit.

To do so, we will complete the following **specific aims**:

**Aim 1:** To assess the independent and combined effectiveness of two classes of mobile technology interventions among patients while on the waitlist for traditional care:

- (a) App-based cognitive behavioral and mindfulness interventions
- (b) Enhanced objective, mobile data feedback on mood, sleep, heart rate, and activity levels

**Aim 2:** To use machine learning to identify key predictors of treatment response from mobile technology,

genomic, and environmental data collected from patients receiving:

- (a) Mobile technology interventions while on a waitlist for outpatient mental health care
- (b) Traditional face-to-face psychotherapy, medication, or neuromodulation treatment

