**Table 1: Study Measures and Administration Time Points**

Measure	Areas of Assessment	Administration Schedule
Demographics	Age, Sex, Race, Ethnicity, Education, Housing, Income	Baseline
Zip Code (Current or Permanent Address)	Social Determinants of Health	Baseline
Risky Families Questionnaire	Early Family Environment	Baseline
NEO-Five Factor Inventory (Select items - Neuroticism Items)	Neuroticism (Domain of Personality)	Baseline
Pittsburgh Sleep Quality Index	Sleep Quality And Disturbance	Baseline
Mental Health Symptom Assessment	Mood Self-Report	Daily
Brief Suicide Risk Measure (Czyz, et al., 2016)	Suicide Risk	Weekly
Mental Health App Assessment Questions - (Adapted from Kern, et al., 2018)	Frequency of Use of Mental Health, Physical Activity, and Mindfulness Apps	Baseline 6 weeks 18 weeks 12 months
Patient Health Questionnaire (PHQ-9)	Depression	Baseline 6 weeks 18 weeks 12 months
Positive and Negative Suicide Ideation Inventory (PANSI)	Suicide Risk Assessment	Baseline 6 weeks 18 weeks 12 months

Generalized Anxiety Disorder 7-Item Scale (GAD-7)	Anxiety	Baseline 6 weeks 18 weeks 12 months
Posttraumatic Stress Disorder Checklist (PCL-5) with PC-PTSD stem question	Post-Traumatic Stress Disorder	Baseline 6 weeks 18 weeks 12 months
Alcohol, Smoking, and Substance Involvement Screening Test (ASSIST)	Substance Use (excluding opioid use)	Baseline 6 weeks 18 weeks 12 months
Current Opioid Misuse Measure (COMM)	Opioid Misuse	Baseline 6 weeks 18 weeks 12 months
Interpersonal Support Evaluation List (ISEL-12)	Brief Social Support Inventory	Baseline 6 weeks 18 weeks 12 months
Satisfaction and Engagement with Care	Self-reported satisfaction with care and reasons for no-shows	18 weeks
Numerical Rating Pain Intensity Scale (NRS)	Pain	Baseline 6 weeks 18 weeks 12 months

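### Arm comparisons are planned as unadjusted t-tests and chi-square tests, although eight scales are scheduled at baseline and three follow-ups; adjusting for baseline would give narrower intervals from the same data

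*Combined protocol and SAP*

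**What the plan says.** The Analysis Plan section describes univariate summaries, "bivariate statistical tests of association" and graphs. Categorical outcomes get a chi-square test; for the rest, "with outcomes that are continuous, we will use t-tests to make comparisons". Means and standard deviations are to be given for "outcomes measures at each assessment and also for change scores", so the t-test could be on either scale. The only regression in the section relates genetic variants to baseline PHQ. No covariate, longitudinal model or missing-data method is given for the comparisons.

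The section does not say which groups are compared. Two places point to the arms. It says of the data that "This will assess responsiveness to the interventions", and Aim 1 in the Objectives is "To assess the independent and combined effectiveness of two classes of mobile technology interventions", to be met by a Phase 1 that randomises to three groups. No other analysis for Aim 1 appears.

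Table 1 gives the schedule "Baseline 6 weeks 18 weeks 12 months" to eight scales: PHQ-9, PANSI, GAD-7, PCL-5, ASSIST, COMM, ISEL-12 and the pain NRS. One entry reads "Posttraumatic Stress Disorder Checklist (PCL-5) with PC-PTSD stem question", so the PCL-5 may not be scored for everyone. The app-use questions share the schedule but are not a scale.

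**The concern.** A t-test on the follow-up score ignores the baseline value. A t-test on the change score uses baseline, but with a fixed coefficient of 1 instead of the one the data support. Both leave variance in the comparison that a baseline covariate would remove, on every continuous scale.

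There is a second, conditional issue. A visit-by-visit test drops anyone without a score at that visit, including those who answered an earlier follow-up. The Withdrawing section ends data collection at withdrawal, so some later scores will be absent; no rate or pattern is given. If absence is related to earlier scores, and differently so between arms, the test compares differently selected groups.

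**Working it through.** **Inputs.** From the document: 4,500 participants (Screening and Recruitment), three arms, and a baseline plus three follow-ups. There is no power calculation to reproduce. Assumed: baseline/follow-up correlation r = 0.3, 0.5 or 0.7, equal variance at each visit, and equal allocation where a per-arm number is needed. Triplets below are in that order of r.

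**Precision at one visit, complete data.** Set the variance of the arm difference for the follow-up score to 1.
- Change score: 2(1 − r) = 1.40 / 1.00 / 0.60.
- Baseline-adjusted: 1 − r² = 0.91 / 0.75 / 0.51.
- Narrowing against the follow-up score: 1 − √(1 − r²) = 0.046 / 0.134 / 0.286.
- Narrowing against the change score: the variance ratio is (1 − r²)/[2(1 − r)] = (1 + r)/2, so 1 − √((1 + r)/2) = 0.194 / 0.134 / 0.078.

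Adjustment is the more precise for any r strictly between 0 and 1.

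**In participants.** If all 4,500 are randomised and analysed, the gain is 4,500 × [1/(1 − r²) − 1] = 445 / 1,500 / 4,324 against the follow-up score, and 4,500 × [2/(1 + r) − 1] = 2,423 / 1,500 / 794 against the change score. These are upper bounds. A two-arm contrast under equal allocation uses 3,000 people, which gives 297 / 1,000 / 2,882 and 1,615 / 1,000 / 529.

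**What repeated measures adds.** At one visit with complete data it adds nothing beyond baseline adjustment. With an assumed 30% missing at 12 months, unrelated to scores, and a common correlation of 0.5, the variances are 1.43 (t-test on completers), 1.07 (baseline adjustment on completers) and 1.02 (repeated-measures model).

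**Drop-out bias, assumed scenarios.** True benefit 0.10 SD at 18 weeks; 1,500 per arm; higher score is worse; 6-week scores all observed; 6–18 week correlation ρ = 0.5 / 0.6 / 0.8. Response at 18 weeks has logit 0.4 − 0.5 × the 6-week score in the named arm (about 60% respond). 2,000 runs, Monte Carlo standard error at most 0.0013.

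| Dependence on | Arm | Follow-up t-test | Change t-test | Repeated-measures model |
|---|---|---|---|---|
| 6-week score | comparator | 0.006 / −0.016 / −0.054 | 0.064 / 0.081 / 0.082 | 0.102 / 0.100 / 0.101 |
| 6-week score | treated | 0.193 / 0.211 / 0.248 | 0.139 / 0.118 / 0.118 | 0.100 / 0.099 / 0.100 |
| 6-week score | both equally | 0.097–0.101 | 0.097–0.101 | 0.097–0.101 |
| baseline, then 6-week score | comparator | 0.009 / −0.024 / −0.065 | 0.147 / 0.137 / 0.117 | 0.099–0.101 |
| baseline, then 6-week score | treated | 0.190 / 0.219 / 0.261 | 0.056 / 0.063 / 0.082 | 0.099–0.101 |
| unobserved 18-week score | comparator | −0.093 / −0.093 / −0.094 | −0.036 / 0.004 / 0.043 | −0.041 / −0.015 / 0.036 |
| unobserved 18-week score | treated | 0.288 / 0.287 / 0.287 | 0.231 / 0.192 / 0.156 | 0.238 / 0.210 / 0.161 |

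The first two rows can be checked by hand. Selection on the 6-week score lowers its mean among responders by about 0.19 SD. The follow-up mean moves by 0.19ρ and the change mean by 0.19(ρ − r). At r = 0.3 with comparator drop-out this gives 0.10 − 0.19 × 0.5 = 0.005 and 0.10 − 0.19 × 0.2 = 0.062. When ρ = r the change-score bias vanishes; simulated values in that case were 0.099 / 0.098 / 0.103 (600 runs). Selection on baseline moves the change mean in the opposite direction, by a factor r − 1, which is why the direction flips in the two-step rows.

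Baseline adjustment alone on 18-week responders does not cure this. It gave 0.023 / 0.032 / 0.040 (comparator) and 0.177 / 0.165 / 0.158 (treated) when drop-out depended on the 6-week score.

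**Categorical outcome.** True risk difference 3.4 points, drop-out on the 6-week score in the comparator arm: unadjusted −0.1 / −0.7 / −2.1, baseline-only logistic 0.5 / 0.9 / 1.0, imputation using the 6-week score 3.3 / 3.4 / 3.4.

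**The case against.** The best case for the plan is that its section puts feasibility, acceptability and the spread of candidate outcomes first, and says "This is a primary outcome for future work" after its sentence on responsiveness. Means, standard deviations and simple tests serve that goal. This stands in part: that the t-tests compare arms is an inference, and the comparisons may be meant as exploratory. It does not remove the point, because feasibility is described as one primary goal, and Aim 1 is comparative effectiveness with no other analysis.

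It is also fair that the planned tests are valid with complete data, and that the single-visit gain belongs to baseline adjustment and not to the repeated-measures model.

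A reader might go further and infer that the planned tests will give biased or reversed results. The document does not support that. It gives no drop-out rate or pattern. Reversal under observed-score drop-out needs arm-specific dependence and, in the scenarios run, occurs only with the follow-up-score test. The bias of the change-score test depends on the arm, the mechanism and the correlations, and is essentially nil when ρ = r. Nor should the survey items omitted near clinic appointments be counted as lost: the Self-Report Surveys section treats them as overlapping with clinic questions, and the answers may be in the health records.

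**Conclusion.** The concern holds as a matter of precision. If the tests compare arms, baseline adjustment narrows intervals by 5 / 13 / 29% or 19 / 13 / 8%, depending on which score the t-test would have used. Those figures rest on the assumed range of r and on equal variances. The participant equivalents also need all 4,500 to be randomised and analysed, so they are ceilings.

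Drop-out bias is secondary and conditional. If the dependence on earlier scores is equal in all arms, the gain is essentially precision only. If drop-out depends on unobserved scores in one arm, the repeated-measures model is biased too. It then beats the follow-up-score test but need not beat the change-score test. The change is advisable; the planned analysis is not invalid without it.

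**What to change.** - State that the tests compare randomised arms. For each continuous scale, replace the t-tests with one mixed model for repeated measures in randomised participants with any follow-up score: baseline score by visit, arm by visit, recruitment site, unstructured covariance.
- For categorical outcomes, replace chi-square with a baseline-adjusted logistic model on data multiply imputed by arm from baseline and earlier visits, or with a repeated-measures logistic model.
- Name the contrasts that the three arms allow: App+EF+SF against EF+SF, App+EF+SF against App+SF, and App+SF against EF+SF. Label them exploratory unless a primary outcome, visit and contrast are named.
- Before defining the analysis set, reconcile the Phase 1 and App-Based Interventions sections. The first says that people with under two weeks to their appointment are still randomised to the three groups; the second places them outside the initial randomisation.
- State the missing-at-random assumption and add a sensitivity analysis for drop-out that depends on unobserved scores.

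The cost is plan wording and modest programming, with no new participants, visits or measures. The downside is reliance on missing at random, which the sensitivity analysis is there to probe.
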